9.4 Renal safety monitoring

Renal events are defined as one of the following:

- confirmed (after ≥ 24h) increase in serum creatinine of ≥ 25% compared with baseline during normal hydration status
- new onset (≥1+) proteinuria, hematuria or glucosuria; or as a
- doubling in the urinary albumin-creatinine ratio (ACR) or urinary protein-creatinine ratio (PCR) (if applicable).

The following two categories of abnormalities/adverse events have to be considered during the course of the study:

- Serum creatinine triggers that will require follow up and repeat assessments of the abnormal laboratory parameter

- Urine dipstick triggers that will require follow up and repeat assessments of the abnormal laboratory parameter

Table 9-3 Specific Renal Alert Criteria and Actions

Renal Event	Actions
Serum creatinine increase 25 – 49% compared with baseline	Confirm 25% increase after 24-48h Follow up within 2-5 days
Serum creatinine increase \geq 50 % compared with baseline	Follow up within 24-48h if possible Consider drug interruption Consider patient hospitalization /specialized treatment
Albumin- or Protein-creatinine ratio increase \geq 2-fold	Confirm value after 24-48h Perform urine microscopy
Albumin-creatinine ratio (ACR) \geq 30 mg/g or \geq 3 mg/mmol; New dipstick proteinuria \geq 1+ Protein-creatinine ratio (PCR) \geq 150 mg/g or >15 mg/mmol	Consider drug interruption / discontinuation
New dipstick glucosuria \geq 1+ not due to diabetes	Blood glucose (fasting) Perform serum creatinine, ACR
New dipstick hematuria not due to trauma	Urine sediment microscopy Perform serum creatinine, ACR
Document contributing factors: co-medication, other co-morbid conditions, and additional diagnostic procedures performed in the CRF	

Monitor patient regularly (frequency at investigator's discretion) until one of the following:

Event resolution: (sCr within 10% of baseline or protein-creatinine ratio within 50% of baseline)

Event stabilization: sCr level with $\pm 10\%$ variability over last 6 months or protein-creatinine ratio stabilization at a new level with $\pm 50\%$ variability over last 6 months.

9.5 Pregnancy reporting

To ensure patient safety, each pregnancy in a patient on study drug must be reported to Novartis within 24 hours of learning of its occurrence. The pregnancy should be followed up to determine outcome, including spontaneous or voluntary termination, details of the birth, and the presence or absence of any birth defects, congenital abnormalities, or maternal and/or newborn complications. The study drug must be discontinued, though the patient may stay in the study, if she wishes to do so. All assessments that are considered as a risk during pregnancy must not be performed. The patient may continue all other protocol assessments. Pregnancy must be recorded on a Pharmacovigilance Pregnancy Form and reported by the investigator to the local Novartis CMO & PS Department. Pregnancy follow-up should be recorded on the same form and should include an assessment of the possible relationship to the Novartis study drug of any pregnancy outcome. Any SAE experienced during pregnancy must be reported on an SAE Report Form.

Pregnancy outcomes must be collected for the female partners of any males who took study treatment in this study. Consent to report information regarding these pregnancy outcomes should be obtained from the mother.

9.6 Early phase safety monitoring

The Investigator will monitor adverse events in an ongoing manner and inform the Sponsor of any clinically relevant observations. Any required safety reviews will be made jointly between medically qualified personnel representing the Sponsor and Investigator. Such evaluations may occur verbally, but the outcome and key discussion points will be summarized in writing (e-mail) and made available to both Sponsor and all Investigator(s). Criteria pertaining to stopping the study/treatment or adapting the study design are presented above.

When two or more clinical site(s) are participating in the clinical study, the Sponsor will advise the Investigator(s) at all sites in writing (e-mail) (and by telephone if possible) of any new, clinically relevant safety information reported from another site during the conduct of the study in a timely manner.

10 Data review and database management

10.1 Site monitoring

Before study initiation, at a site initiation visit or at an investigator's meeting, a Novartis representative will review the protocol and CRFs with the investigators and their staff. During the study Novartis employs several methods of ensuring protocol and GCP compliance and the quality/integrity of the sites' data. The monitor will visit the site to check the completeness of patient records, the accuracy of entries on the CRFs, the adherence to the protocol and to Good Clinical Practice, the progress of enrollment, and to ensure that study drug is being stored, dispensed, and accounted for according to specifications. Key study personnel must be available to assist the monitor during these visits.

The investigator must maintain source documents for each patient in the study, consisting of case and visit notes (hospital or clinic medical records) containing demographic and medical information, laboratory data, electrocardiograms, and the results of any other tests or assessments. All information on CRFs must be traceable to these source documents in the patient's file. The investigator must also keep the original informed consent form signed by the patient (a signed copy is given to the patient).

The investigator must give the monitor access to all relevant source documents to confirm their consistency with the CRF entries. Novartis monitoring standards require full verification for the presence of informed consent, adherence to the eligibility criteria, documentation of SAEs, and the recording of data that will be used for all primary and safety variables. Additional checks of the consistency of the source data with the CRFs are performed according to the study-specific monitoring plan. No information in source documents about the identity of the patients will be disclosed.

10.2 Data collection

Designated investigator staff will enter the data required by the protocol into the Electronic Case Report Forms using fully validated software that conforms to 21 CFR Part 11 requirements. Designated investigator site staff will not be given access to the EDC system until they have been trained. Automatic validation programs check for data discrepancies and, by generating appropriate error messages, allow the data to be confirmed or corrected before transfer of the data to the CRO working on behalf of Novartis. The Investigator must certify that the data entered into the Electronic Case Report Forms are complete and accurate. After database lock, the investigator will receive a CD-ROM or paper copies of the patient data for archiving at the investigational site.

Data not requiring a separate written record will be defined in the SOM and assessment schedule and can be recorded directly on the CRFs. All other data captured for this study will have an external originating source (either written or electronic) with the CRF not being considered as source.

All data should be recorded, handled and stored in a way that allows its accurate reporting, interpretation and verification.

Novartis staff review the data entered into the eCRFs by investigational staff for completeness and accuracy and instruct the site personnel to make any required corrections or additions. Queries are sent to the investigational site using an electronic data query. Designated investigator site staff is required to respond to the query and confirm or correct the data. If the electronic query system is not used, a paper Data Query Form will be faxed to the site. Site personnel will complete and sign the faxed copy and fax it back to Novartis staff who will make the correction to the database.

Concomitant medications entered into the database will be coded using the WHO Drug Reference List, which employs the Anatomical Therapeutic Chemical classification system. Medical history/current medical conditions and adverse events will be coded using the Medical dictionary for regulatory activities (MedDRA) terminology.

Laboratory samples will be processed centrally and the results will be sent electronically to Novartis (or a designated CRO).

Randomization codes and data in reference to dispensing of study drug(s) to the patient and all IRT recorded dosage changes will be tracked using Interactive Response Technology (IRT). The system will be supplied by a vendor, who will also manage the database. The database will be sent electronically to Novartis (or a designated CRO).

Each occurrence of a code break via IRT will be reported to the clinical team and monitor. The code break functionality will remain available until study shut down or upon request of Novartis.

11 Data analysis

Analysis of the data will be conducted under the direction of Novartis personnel in compliance with internal guidance documents and standards.

11.1 Analysis sets

For all analysis sets, patients will be analyzed according to the study treatment(s) received.

The safety analysis set will include all patients that received any study drug.

The PK analysis set will include all patients with at least one available valid (i.e., not flagged for exclusion) PK concentration measurement, who received study drug, and experienced no protocol deviations with relevant impact on PK data.

Corporate Confidential Information

11.2 Patient demographics and other baseline characteristics

All data for background and demographic variables will be listed by cohort, treatment and patient. Summary statistics will be provided for all patients, as well as for each treatment. Data from patients receiving placebo may be pooled only for cohort 1 and 2 of the study.

Relevant medical history, current medical conditions, results of laboratory screens, drug tests and any other relevant information will be listed by treatment (treatment sequence for cohort 3) and patient.

11.3 Treatments (study drug, rescue medication, other concomitant therapies, compliance)

Use of rescue and/or concomitant medications and data on administration of study drug will be listed by cohort, treatment (treatment sequence for cohort 3), and patient.

11.4 Analysis of the primary variable(s)

11.4.1 Variable(s)

The primary variable is occurrence of an adverse event for cohort 1 and cohort 2 and evaluate the pharmacodynamic response as reflected in percent of predicted FEV1 for cohort 3 of multiple doses of inhaled QBW276 in CF patients.

11.4.2 Statistical model, hypothesis, and method of analysis

Cohort 1 and Cohort 2: All information obtained on adverse events will be listed by cohort, treatment and patient. For each cohort, adverse events will be counted within each cohort/dose-level, by treatment received and corresponding percentages will be tabulated.

Data from subjects receiving placebo may be pooled for cohorts 1 and 2 of the study. The numbers and percentages will be tabulated by body system, preferred term and severity. A patient with multiple adverse events within a body system is only counted once towards the total of this body system.

All other safety assessments including ECG, vital signs and laboratory data will be listed by cohort, treatment, patient, and visit/time and if ranges are available abnormalities (and relevant orthostatic changes) will be flagged. Summary statistics will be provided by treatment and visit/time.

Drug concentrations will be listed by treatment, patient and visit/sampling time point. Descriptive summary statistics will be provided by treatment and visit/sampling time point. Summary statistics will include mean (arithmetic and geometric), SD, CV (arithmetic and geometric), median, minimum and maximum. Concentrations below the LLOQ will be treated as zero in summary statistics. A geometric mean will not be reported if the dataset includes zero values.

Pharmacokinetic parameters in Cohorts 1 and 2 will be calculated as described in [Section 8.5](#) and will be listed by treatment and patient. Descriptive summary statistics will include mean (arithmetic and geometric), SD, and CV (arithmetic and geometric), median, minimum and maximum. An exception to this is Tmax where median, minimum and maximum will be presented. Individual concentration-time profiles and mean profiles with SD bars will be presented for Day 1 and Day 7 or 14 in Cohorts 1 and 2.

Cohort 3:

The percent of predicted FEV1 may be put into a mixed effects model. Percent of predicted FEV1 values measured on Day 7, 14, 21 and 28 of each treatment period at the study site will be analyzed using a mixed effects model for repeated measurements. The model will include fixed effects for period, time (Days 7, 14, 21, 28), Corporate Confidential Information treatment and treatment by time. Subject will be included as a random effect and time will be repeated within each patient by period interaction term. Subject-average baseline and period-adjusted baseline will be fitted as covariates. An unstructured covariance matrix will be applied. Kenward Roger options will be used to calculate the degrees of freedom in all Proc Mixed analysis.

The subject average baseline will be derived as the average of their pre-dose assessments from each period. Period adjusted baseline will be calculated for each subject and for each period, as the difference between the period baseline and the subject average baseline, i.e. value of period baseline – value of average baseline ([Kenward and Roger 1997](#)).

The final model estimates will include the LSmean for each treatment together with standard error (SE), the adjusted mean difference between treatments, and 80% two-sided confidence intervals and P-value for the differences. These will be calculated at all time points, and specifically at the primary time point of interest (Day 28) using Placebo as the reference treatment.

The results of analysis will also be presented in a graphical representation showing the estimated mean differences to placebo and their confidence intervals per time point.

Summary statistics and graphical representations of percent of predicted FEV1 will be presented by treatment group and time.

No adjustments for multiplicity will be applied for this exploratory study.

Additional exploratory analyses such as responder analyses and analysis by gender may be performed. Detailed statistical methods will be discussed in the Statistical Analysis Plan.

11.4.3 Handling of missing values/censoring/discontinuations

Cohorts 1 and 2: Patients withdrawn for reasons other than safety and tolerability prior to completion of the Day 7 or 14 assessments may be replaced to gather sufficient data to perform an informed decision on dose selected for the subsequent cohort.

Cohort 3: The repeated measures analysis includes all available information in terms of measurements at all times. If missing measurements are missing at random, an analysis of the available data provides consistent estimates of model parameters. Alternative assumptions may be explored to investigate the robustness of the results under plausible non-Missing at Random situations. Reasons for dropouts will be explored.

Where data has values below and above limits of quantification then the following rule will apply.

In the summary tables, the frequency (n, %) of values below the LLOQ and above the ULOQ, respectively, will be included.

Any values below the limit of quantification will be analyzed as 0.5*the lower limit, both in the descriptive and the model analysis. Any values above the limit of quantification will be analyzed as 1.0*the upper limit, both in the descriptive and the model analysis.

No other imputation of missing data is allowed.

11.5 Analysis of secondary and exploratory variables

Corporate Confidential Information

11.5.2 Safety

Vital signs

All vital signs data will be listed by cohort, treatment (treatment sequence for cohort 3), patient, and visit/time and if ranges are available abnormalities (and relevant orthostatic changes) will be flagged. Summary statistics will be provided by treatment and visit/time.

ECG evaluations

All ECG data will be listed by cohort, treatment (treatment sequence for cohort 3), patient and visit/time, abnormalities will be flagged. Summary statistics will be provided by treatment and visit/time.

Clinical laboratory evaluations

All laboratory data will be listed by cohort, treatment (treatment sequence for cohort 3), patient, and visit/time and if normal ranges are available abnormalities will be flagged. Summary statistics will be provided by treatment and visit/time.

Adverse events

For cohort 3, all information obtained on adverse events will be displayed by cohort, treatment sequence and patient.

The number and percentage of patients with adverse events will be tabulated by body system and preferred term with a breakdown by treatment. An adverse event starting in one period and continuing into the next period is counted only in the onset period. A patient with multiple adverse events within a body system and treatment period is only counted once towards the total of this body system and treatment.

Corporate Confidential Information

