For Cohort 3, patients will be randomized to one of two treatment sequences: QBW276 in Period 1 and Placebo in Period 2 or Placebo in Period 1 and QBW276 in Period 2. Based on drop-out rates observed during conduct of the study, up to 40 patients will be randomized to ensure that at least 24 patients complete the study. After a 45 day screening period, patients who meet all inclusion and exclusion criteria will receive drug for 4 weeks and placebo for 4 weeks, separated by a washout period of approximately 3 to 4 weeks in patients who cycle inhaled antibiotics. Washout period may be shortened to 2 weeks in patients who do not cycle inhaled antibiotics. QBW276 will be administered on top of the patient's usual standard of care medications. For patients on cyclic inhaled antibiotics, baseline for periods 1 and 2 will commence on approximately day 7 (0/+3) of the patient's standard of care cyclic inhaled antibiotic regimen. Patients who use the same inhaled antibiotic throughout the year may start the study on any antibiotic day.

Screening and baseline visits for cohort 3 will be similar to the respective visits in cohorts 1 and 2. On Day 1 of cohort 3, pre-dose safety, efficacy Corporate Confidential Information will be performed. Following the pre-dose procedures eligible patients will be dosed for up to 28 days. Post-dose evaluations will include routine safety evaluations and blood for PK assessments. The patients will be asked to return to the study site for follow-up visits on Days 7, 14, 21, and 28 after which they will undergo an approximately 3 to 4 week wash-out period (may be shortened to 2 weeks in patients who do not cycle inhaled antibiotics) prior to cross-over to the opposite arm, and follow a similar visit schedule until End of Study assessment approximately 7 days after the last visit in the second period. All patients will undergo the same assessments regardless of their dose.

Efficacy will be evaluated by spirometry and responses to the respiratory domain of the CFQ-R. Safety will be monitored by assessment of vital signs, physical examination, ECG, clinical laboratory evaluations (hematology, blood chemistry, and urinalysis), urine electrolytes, aldosterone in plasma, and monitoring of adverse events (AEs) throughout the study.

Corporate Confidential Information

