3. its duration (start and end dates) or if the event is ongoing an outcome of not recovered/not resolved should be reported.
4. whether it constitutes a serious adverse event (SAE) See [Section 9.2](#) for definition of SAE
5. action taken regarding [study/investigational] treatment(select as appropriate).

All adverse events should be treated appropriately. Treatment may include one or more of the following:

- no action taken (i.e. further observation only)
- study treatment dosage adjusted/temporarily interrupted
- study treatment permanently discontinued due to this adverse event
- concomitant medication given
- non-drug therapy given
- patient hospitalized/patient's hospitalization prolonged

6. its outcome (not recovered/not resolved; recovered/resolved; recovering/resolving, recovered/resolved with sequelae; fatal; or unknown)

Once an adverse event is detected, it should be followed until its resolution or until it is judged to be permanent, and assessment should be made at each visit (or more frequently, if necessary) of any changes in severity, the suspected relationship to the study drug, the interventions required to treat it, and the outcome.

Information about common side effects already known about the investigational drug can be found in the Investigator Brochure (IB) or Core Data Sheet (for marketed drugs) or will be communicated between IB updates in the form of Investigator Notifications. This information will be included in the patient informed consent and should be discussed with the patient during the study as needed.

The investigator should also instruct each patient to report any new adverse event (beyond the protocol observation period) that the patient, or the patient's personal physician, believes might reasonably be related to study treatment. This information should be recorded in the investigator's source documents; however, if the AE meets the criteria of an SAE, it must be reported to Novartis.

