9.2 Serious adverse event reporting

9.2.1 Definition of SAE

An SAE is defined as any adverse event (appearance of (or worsening of any pre-existing) undesirable sign(s), symptom(s) or medical conditions(s) which meets any one of the following criteria:

- is fatal or life-threatening
- results in persistent or significant disability/incapacity
- constitutes a congenital anomaly/birth defect

- requires inpatient hospitalization or prolongation of existing hospitalization, unless hospitalization is for:
 - routine treatment or monitoring of the studied indication, not associated with any deterioration in condition
 - elective or pre-planned treatment for a pre-existing condition that is unrelated to the indication under study and has not worsened since the start of study drug
 - treatment on an emergency outpatient basis for an event not fulfilling any of the definitions of a SAE given above and not resulting in hospital admission
 - social reasons and respite care in the absence of any deterioration in the patient's general condition
- is medically significant, i.e. defined as an event that jeopardizes the patient or may require medical or surgical intervention.

Life-threatening in the context of a SAE refers to a reaction in which the patient was at risk of death at the time of the reaction; it does not refer to a reaction that hypothetically might have caused death if more severe.

All malignant neoplasms will be assessed as serious under “medically significant” if other seriousness criteria are not met.

Any suspected transmission via a medicinal product of an infectious agent is also considered a serious adverse reaction.

Medical and scientific judgment should be exercised in deciding whether other situations should be considered serious reactions, such as important medical events that might not be immediately life threatening or result in death or hospitalization but might jeopardize the patient or might require intervention to prevent one of the other outcomes listed above. Examples of such events are intensive treatment in an emergency room or at home for allergic bronchospasm, blood dyscrasias or convulsions that do not result in hospitalization or development of dependency or abuse.

All AEs (serious and non-serious) are captured on the CRF, SAEs also require individual reporting to DS&E as per [Section 9.2.2](#).

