## Adverse events

All information obtained on adverse events will be displayed by cohort, treatment group (treatment sequence for cohort 3) and subject.

The number and percentage of subjects with adverse events will be tabulated by body system and preferred term with a breakdown by treatment. A subject with multiple adverse events within a body system is only counted once towards the total of this body system and treatment.

For the legal requirements of ClinicalTrials.gov and EudraCT, two required tables on treatment emergent adverse events which are not serious adverse events with an incidence greater than 5% and on treatment emergent serious adverse events and SAE suspected to be related to study treatment will be provided by system organ class and preferred term on the safety set population.

If for a same patient, several consecutive AEs (irrespective of study treatment causality, seriousness and severity) occurred with the same SOC and PT:

- a single occurrence will be counted if there is  $\leq 1$  day gap between the end date of the preceding AE and the start date of the consecutive AE
- more than one occurrence will be counted if there is  $> 1$  day gap between the end date of the preceding AE and the start date of the consecutive AE.

For occurrence, the presence of at least one SAE / SAE suspected to be related to study treatment / non SAE has to be checked in a block e.g., among AE's in a  $\leq 1$  day gap block, if at least one SAE is occurring, then one occurrence is calculated for that SAE.

The number of deaths resulting from SAEs suspected to be related to study treatment and SAEs irrespective of study treatment relationship will be provided by SOC and PT.

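### The Cohort 3 table counts an adverse event that continues into the next period only in its onset period, with no exception for an event that worsens after crossover

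*Protocol*

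**What the plan says.** Cohort 3 is a two-period crossover: "patients will be randomized to one of two treatment sequences", QBW276 then placebo or placebo then QBW276 (Protocol 3.1). Its adverse events are "tabulated by body system and preferred term with a breakdown by treatment" (Protocol 11.5.2). For events that span the periods, the same section says: "An adverse event starting in one period and continuing into the next period is counted only in the onset period". Individual data are also "displayed by cohort, treatment sequence and patient".

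For Cohorts 1 and 2 the layout differs: "The numbers and percentages will be tabulated by body system, preferred term and severity" (Protocol 11.4.2).

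On recording, Protocol 9.1 has each event followed until it resolves or is judged permanent, and says "assessment should be made at each visit (or more frequently, if necessary) of any changes in severity". Worsening is named as an event only in the SAE definition: "appearance of (or worsening of any pre-existing) undesirable sign(s), symptom(s) or medical conditions(s" (Protocol 9.2.1). No counting rule is attached to it there.

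SAP 7.2 counts a subject once per body system and treatment. It contains neither the onset-period rule nor a rule for worsening. For the registry tables it merges consecutive records separated by no more than one day into a single occurrence; the condition reads "irrespective of study treatment causality, seriousness and severity) occurred with the same SOC and PT". It adds that a merged block containing an SAE yields one occurrence of that SAE.

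**The concern.** Onset-period counting is a reasonable convention for an event that simply continues. It stops being neutral when the event gets worse under the second treatment, because the worsening is new information about that treatment and the table has nowhere to put it. The protocol has severity changes assessed at every visit, but the summary by treatment does not use them.

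Safety and tolerability are part of the secondary objective of Cohort 3 (Protocol 2.2), and this cohort has the longest exposure, 4 weeks against 1 or 2. Aggravation of a symptom already present is one way in which an inhaled drug could do harm. If that happened in a placebo-first patient, the event would sit in the placebo column and be absent from the QBW276 column.

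**Working it through.** The plan gives no figure that depends on this rule, so the check is mainly a comparison of texts.

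**1. What the rule does in each case**

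| Sequence | Event | Counted under |
|---|---|---|
| Either | Starts in Period 1, continues unchanged | Period 1 treatment only (reasonable) |
| Placebo then QBW276 | Starts on placebo, worse on QBW276, same record | Placebo only |
| QBW276 then placebo | Starts on QBW276, worse on placebo, same record | QBW276 only |
| Either | Worsening entered as a new record in Period 2 | Period 2 treatment |

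The second and third rows are the problem. They depend on the worsening staying inside one AE record.

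**2. Is it one record?** Protocol 9.1 treats a severity change as follow-up of the same event. No visible text says that a non-serious worsening opens a new event with its own onset date. Protocol 8.4 leaves recording methods to the site operations manual, which is not available here. One record is therefore the more natural reading, but it is an assumption.

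**3. Would another table show the change?** The Cohort 3 layout is body system, preferred term and treatment. Severity is a dimension of the table for Cohorts 1 and 2 but not here. The listing by sequence and patient does show it.

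**4. What if a new record is opened?** The main table then works. In the SAP's registry occurrence counts, the new record would be merged with the old one if the gap is no more than one day, whatever the severity. If either record is an SAE, the block still yields an SAE occurrence. The SAP does not say which treatment a block spanning two periods belongs to.

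**5. How many patients can be affected?** The event must meet all of these conditions:
- It is new after consent, because earlier conditions are medical history (Protocol 8.2).
- It outlasts a washout of about 3 to 4 weeks, or 2 weeks in patients who do not cycle inhaled antibiotics (Protocol 3.1).
- It leaves the patient eligible at the Period 2 baseline, where the criteria are rechecked (Table 8-1, Cohort 3) and include investigator-judged clinical stability (Protocol 4.1).
- It is not an exacerbation, since those lead to discontinuation (Protocol 7.1).

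Only placebo-first patients can lose an event from the QBW276 column. The documents give no rate for this combination.

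**6. Size per patient.** The Cohort 3 target is 24 completers, with up to 40 randomized. One patient missing from the QBW276 count of a preferred term changes its incidence by:
- 1/24 = 4.2 percentage points with 24 patients treated;
- 1/40 = 2.5 points with 40 patients treated.

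For a body-system total the change occurs only if the patient has no other event of that system counted under QBW276, because each patient counts once per system and treatment.

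**The case against.** The strongest reply is that Protocol 11.5.2 speaks of events that continue and is silent on worsening. If sites are told to open a new record when an event worsens, its onset falls in Period 2 and the main table attributes it correctly. That instruction could be in the site operations manual, and text following the adverse event paragraph in 11.5.2 is redacted. This stands as a limit. It is also a reason to write the convention down, since the visible text points to a single record.

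A reader might infer that the SAP's merging rule closes off the new-record route. It does not. It governs occurrence counts in the registry tables, not the patient counts in the main table, and it keeps an SAE within a merged block.

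A reader might also infer that chronic cystic fibrosis symptoms make this common. The documents do not support that. A symptom that predates consent is medical history, and if it first worsens on QBW276 its AE onset is on QBW276. The conditions in the working narrow the group further.

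Finally, no information is lost. The listings hold the full history of 24 to 40 patients, and neither the stopping rules nor the data monitoring committee's safety monitoring is stated to depend on this table. Cohort 3 safety is descriptive and secondary in a non-confirmatory study. All of this stands and limits the importance of the point. It does not make the table's attribution correct.

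**Conclusion.** The point holds as a gap in the attribution rule of one summary table. Provided that worsening is kept within the original AE record, an event that starts on one treatment and worsens on the other is shown only under the first, and no visible Cohort 3 summary table shows the change in severity.

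The tempting stronger conclusion is that the rule makes QBW276 look safer. The documents do not support it as a general statement. The rule works the same way in both sequences, and an event that starts on QBW276 and worsens on placebo stays with QBW276. A net effect in the drug's favour would require QBW276 to aggravate ongoing events, which cannot be assumed. What can be said is conditional: if it does so in placebo-first patients, that aggravation is left out of the QBW276 column.

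The number affected is probably small and cannot be estimated from the documents. Each patient is worth 2.5 to 4.2 points on a preferred term. This is an inexpensive improvement to the plan, not a threat to its conclusions.

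**What to change.** - **Protocol 11.5.2 and SAP 7.2:** keep onset-period counting for events that continue unchanged. Also count an event under the later period's treatment when its severity or seriousness increases after the first dose of that period, whether the increase is entered as a new row or as a change within the same AE.
- **SAP 7.2:** carry the onset-period rule over. The SAP was written to protocol v02 (SAP 1.2) and omits it.
- **SAP registry occurrence counts:** do not merge records across the first dose of a new period when severity or seriousness has increased. This is consistent with the existing rule that an SAE within a block is counted.

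The cost is wording, one derivation flag and a footnote, because a few events will appear under both treatments. Protocol 9.1 lists start and end dates among the recorded items but does not name a date of severity change, so that date may have to be taken from the visit at which the change was assessed. The rule should be fixed before unblinding, so that no event is reassigned with knowledge of treatment. Nothing in patient management changes.
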